## ABBREVIATIONS AND DEFINITIONS OF TERMS

Abbreviation	Definition
14-HDHA	14-hydroxy docosahexaenoic acid
17-HDHA	17-hydroxy docosahexaenoic acid
18-HEPE	18-hydroxy eicosapentaenoic acid
BMI	Body mass index
CyTOF	Cytometry at time of flight
DHA	Docosahexaenoic acid
EPA	Eicosapentaenoic acid
HDL	high density lipoprotein
LDL	Low density lipoprotein
NSAIDs	non-steroidal anti-inflammatory drugs
PBMC	Peripheral blood mononuclear cells
PCA	Principal component analysis
PHI	Personal health information
PUFA	Polyunsaturated fatty acid
SPMs	Specialized Pro-resolving Mediators

## PROTOCOL SYNOPSIS

Study Title	Immunometabolic Response to Specialized Pro-Resolving Mediators in Obese Humans
Funder	Departmental funds
Clinical Phase	Pilot study
Study Rationale	
Obesity is associated with chronic, low-grade inflammation and impaired immunity, which contributes to the development of metabolic complications such as diabetes, cardiovascular disease, and increased susceptibility to infection due to impaired humoral immunity. The metabolism of immune cells has emerged as a major therapeutic target for improving chronic inflammation. Specialized pro-resolving mediators (SPMs) in particular are lipid-derived metabolites critical in orchestrating the resolution phase of inflammation. However, SPMs are lowered with obesity. The innovation lies in the study of SPMs as therapeutic agents for immune resolution of chronic inflammation that can lead to an improved humoral immune response in the obese. Our first objective is to establish the concentration of SPMs in plasma, serum and peripheral blood mononuclear cells (PBMCs) of obese subjects in response to dietary supplementation of SPMs (aim 1a). We will further determine the immunological fitness of the leukocyte pool, specifically examining B cell antibody production in response to ex-vivo stimulation (aim 1b). Finally, we will correlate metabolic profiles with SPM concentrations (aim 2). Overall, this will help us determine whether SPM supplementation mitigates the impaired humoral immune response of obese subjects and determine the use of SPMs as potential therapeutic agents for the obese.

Study Objective(s)	
Primary Aim 1: To compare immunological fitness pre- and post-oral SPM administration in the obese.
 

• Aim 1a: To quantify SPM concentrations in plasma (pg/mL), serum (pg/mL) and PBMCs before and after SPM supplementation.

• Aim 1b: To measure antibody responses of B cells in PBMC pool with in vitro stimulation and cytokine production before and after SPM supplementation.

 
Secondary Aim 2: To compare metabolic profiles pre- and post-supplementation in response to an oral dose of SPMs in the obese.
 

• Aim 2a: To measure fasting insulin (ng/dL) and fasting glucose (mg/dL) before and after intervention.

• Aim 2b: To correlate pre- and post- metabolic measurements with measured pre- and post- SPM concentrations.

Test Article(s) (If Applicable)	The 'SPM Active' dietary supplement will be supplied by Metagenics for intervention.
Study Design	A non-randomized uncontrolled clinical trial with convenience sampling. A total of 24 individuals (12 males & 12 females) will be selected against inclusion/exclusion criteria. Pre- and post-intervention measurements will be collected and analyzed.
Subject Population key criteria for Inclusion and Exclusion:	
Inclusion Criteria
 
 
1. Male and (post-menopausal) female subjects age 50-65 years with BMI 30-40 (obese) who are euglycemic and pre-diabetic
 
 
Exclusion Criteria
 
 
1. Subjects with active autoimmune disease, liver disease, coagulopathy, hypothyroidism, known allergy to fish or shellfish, those taking active asthma medications, anticoagulants, estrogen, testosterone, daily aspirin or NSAIDs, anyone with inability to give informed consent
 
2. Subjects receiving immunomodulatory or immunosuppressant therapy, with known active malignancy or undergoing treatment for malignancy, and those consuming n-3 PUFA supplements or high consumption of fatty fish (>2 servings per week)
 

Number Of Subjects	24
Study Duration	The entire study is expected to last 6-9 months. This includes an enrollment period of 3-4 months and data analysis.
Study Phases Screening Study Treatment Follow-Up	
(1) Screening: Screening for eligibility will be performed by [name] and his designated study coordinator at UNC Family Medicine Center during standard pre-operative checkups in a private, closed-door room. Subjects will be asked questions orally during the primary visit to determine if eligibility criteria are met, at which time informed consent and HIPPA authorization will be obtained.
 
(2) Intervention: The intervention is the dietary supplement 'SPM Active' supplied by Metagenics. All subjects will be administered 4 capsules per day for 4 weeks +/- 2-4 days. 12-hour fasting blood and serum will be drawn pre- and post-intervention for each subject by a licensed phlebotomist at the UNC Family Medicine Lab and under the direction of [name].
 
(3) Follow-Up: The study coordinator will follow up twice by phone at the end of week 1 and week 3 of supplementation and relay any health concerns to [name] who may determine if an in-person visit is necessary. Following 4 weeks intervention, patients will discontinue supplementation follow up in a routine manner as designated by their UNC Family Medicine physician.

Efficacy Evaluations	If SPM administration does not lead to increased uptake of SPMs in PBMCs or serum with the first 9 subjects, then we will not conduct CyTOF. Instead, we will spend the funds in conducting a pilot metabololipidomic study of 9 subjects of one sex to determine if 8 weeks of intervention leads to an elevation in the three metabolites of interest. We envision no technical limitations to the study as all the proposed protocols are optimized.
Safety Evaluations	While adverse events are unlikely, if 50% or more of total study participants report intolerable adverse reactions from taking the supplement, we will stop the study.
Sample Size Rationale	The primary aim of the study is designed and powered to measure an increase in 18-HEPE, 17-HDHA, and 14-HDHA in Aim 1. Additional measures in Aim 2 are exploratory, but necessary for future grant applications to demonstrate the feasibility of the approach. At a family-wise error rate of 5% controlling for testing of three metabolites mentioned above, n=9 will provide more than 80% power to detect a 50%-fold change increase in metabolite levels within each subject. We are assuming a similar effect size for both males and females and are doubling the sample size (n=18, 9 per sex) to allow us to subset the data in case we find divergent results between sexes. To account for possible loss-to-follow up, we increased the sample size to 24 (n=12 male + 12 female). Power analysis was conducted assuming a paired t-test on pre- and post-treatment metabolite levels for three pre-specified metabolites. Expected variability of within subject differences in metabolite levels was assessed from a previous dataset and the median standard deviation was calculated across all metabolites.  Power analyses were calculated by [name] in the UNC Department of Biostatistics.
Statistical & Analytic Plan	Generally, most datasets will be assessed for normality and homogeneity of variance using the Shapiro-Wilks test and Bartlett test respectively. However, normality will also be assessed via a qqplot of the standardized residuals and we will visualize the distribution of our data with a histogram. In addition, to corroborate the Bartlett test we will check the homogeneity of variance of the residuals (homoscedasticity) using a scale-location plot where the square root of the standardized residuals is plotted. Data that passes both assumptions will be analyzed via a paired two sample Student T-test. Data that fails the assumption of heteroscedasticity will be analyzed using a paired Welch T-test. Another alternative would be to apply a log or square root transformation to achieve heteroscedasticity or approach a Gaussian distribution. However, if the data still fails the assumptions of normality and heteroscedasticity it will be analyzed with a paired Wilcoxon rank sum test. All p-values from these

---

analyses will undergo either a Bonferroni or Benjimini-Hochberg p-value adjustment at a 5% false discovery rate.

---

**DATA AND SAFETY  
MONITORING PLAN**

Data will be kept on an encrypted desktop computer protected by multiple passwords in a lab, located on a hall protected by card access in Michael Hooker Research Center, Chapel Hill, NC. De-identified data will be stored on REDCap for use by research team personnel only. Data management will be performed by the PI and the study coordinators. All data acquisition will meet HIPPA and confidentiality standards. The PIs will be responsible for monitoring and reviewing subject data, lab results, study progress, subject safety and confidentiality, and the accuracy and security of the emerging data. They will also be responsible for running the assays and entering all data into redcap for statistical analysis. The co-I, [name], will follow-up with patients as necessary; his contact information and that of the study coordinator will also be given to the study subjects.

---

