#### **4.6 Subject Completion/ Withdrawal procedures**

Subjects will be compensated \$250 cash for their participation and completion of the study (\$100 at baseline visit + \$150 at week 4 visit upon completion). No prorated compensation will be applied for this pilot study. This amount of compensation is not deemed coercive; the incentive is meant to compensate subjects for their time in the study which include two study visits, two phone visits, and two blood draws.

This is a voluntary research study. Refusal to participate or withdrawal of participation and/or consent can occur at any time, for any reason. Subjects may be withdrawn if: (1) they experience intolerable adverse reactions or allergic reaction to study supplement or (2) are not at least 90% compliant with taking study supplement during the 4 weeks active phase. In the event of withdrawal, all personal health information (PHI), electronic or hard copy, will be immediately purged and permanently destroyed. Withdrawal or

refusal will not influence ability, timing, or quality of clinical care, type of clinical care administered, standing with UNCHC system, or ability to participate in future research studies. The investigators also have the right to stop participation at any time. This could be because participants have chosen to stop supplementation, or have failed to follow instructions or because the entire study has been stopped.

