#### **4.7 Screen failure procedures**

Study participants will be checked to determine if they meet the inclusion and exclusion criteria. Those that are not eligible will be excluded from the study. If the study coordinators are not able to contact study subjects in the follow-up phone calls they will be considered as “loss to follow-up” and no longer enrolled in the study.

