#### **5.1 Efficacy Evaluation**

There will be no efficacy evaluation due to the pre-/post- study design, which requires that data be obtained through the end of the clinical trial. However, the study may be stopped due to safety concerns (see safety evaluation section 5.2).

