### **6.4 Sample Size and Power**

Experimental rigor is ensured through the analyses of blinded samples. The study is designed and powered to measure an increase in 18-HEPE, 17-HDHA, and 14-HDHA in Aim 1. Additional measures in Aim 2 are exploratory, but necessary for future grant applications to demonstrate the feasibility of the approach. At a family-wise error rate of 5% controlling for testing of three metabolites mentioned above, n=9 will provide more than 80% power to detect a 50%-fold change increase in metabolite levels within each subject. We are assuming a similar effect size for both males and females and are doubling the sample size (n=18, 9 per sex) to allow us to subset the data in case we find divergent results between sexes. To account for possible loss to follow-up, we will increase sample size from 18 to 24 (n=12 male + 12 female). Power analysis was conducted assuming a paired t-test on pre- and post-treatment metabolite levels for three pre-specified metabolites. Expected variability of within subject differences in metabolite levels was assessed from a previous dataset and the median standard deviation was calculated across all metabolites. Power analyses were calculated by [name] in the UNC Department of Biostatistics.

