### **6.5 Interim Analysis**

Given the pre-/post- design of the study, doing an interim analysis in the middle of the study is not feasible, for we will have to obtain and compare pre- and post- data. Additionally, the metabololipidomics analyses that

we are performing will take several months to complete. Finally, with the small number of subjects, this study is not expected to span a long period of time.

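### Does the CyTOF decision based on the first 9 subjects conflict with the statements that there is no efficacy evaluation and no interim analysis?

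*Combined protocol and SAP*

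**What the plan says.** Three places in the combined protocol and SAP bear on this.

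- **Synopsis, Efficacy Evaluations.** The row states that if supplementation "does not lead to increased uptake of SPMs in PBMCs or serum with the first 9 subjects, then we will not conduct CyTOF". The money would then pay for a separate lipidomic pilot in 9 subjects of one sex. The row goes on to refer to the three metabolites that the study is about.
- **Section 5.1.** "There will be no efficacy evaluation due to the pre-/post- study design", because data are needed to the end of the trial. The next sentence is: "However, the study may be stopped due to safety concerns".
- **Section 6.5.** "doing an interim analysis in the middle of the study is not feasible", since pre and post data must both be in hand and the lipidomic assays take several months.

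The number 9 is also the plan's powered size. Section 6.4 states that "n=9 will provide more than 80% power to detect a 50%-fold change increase in metabolite levels within each subject", using a paired t-test with 5% family-wise error over 18-HEPE, 17-HDHA and 14-HDHA. On loss it says: "To account for possible loss to follow-up, we will increase sample size from 18 to 24". Section 4.6 allows withdrawal of subjects who "are not at least 90% compliant with taking study supplement during the 4 weeks active phase", and Section 4.7 removes those who cannot be reached by phone.

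**The concern.** The synopsis and Section 5.1 use almost the same heading and appear to say opposite things. One uses early lipidomic results to make a decision; the other says no such evaluation takes place. Section 6.5 then gives a practical reason why early results could not be had. SPM concentration is the powered Aim 1 outcome, so an unplanned look at it would normally raise questions about who sees the data and whether the final test is affected.

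Two terms of the rule are also loose. The phrase about the first 9 subjects does not say whether they must have completed, although the trial as a whole carries an allowance for loss. Increased uptake has no stated threshold, and it is not said whether PBMCs and serum must both rise or whether either is enough. Section 3.1 names only plasma and PBMCs as the measured matrices, which seems to leave serum out. On that view, the same data could lead to CyTOF being run or to its money being moved.

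**Working it through.** **1. Can the texts hold together?** Section 6.5 excludes an analysis in the middle of the study. The synopsis rule has no date. Inputs: 3-4 months of enrolment for 24 subjects (Section 3.3), 4 weeks of supplementation, several months for the assay (Section 6.5). Assumptions: even accrual, samples sent when the ninth subject finishes, 2-4 months for the assay, 30.4 days per month.

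- Ninth subject enrolled: 3 × 9/24 = 1.125 to 4 × 9/24 = 1.5 months.
- Ninth subject finished: add 28/30.4 = 0.92, giving 2.05 to 2.42 months.
- First-9 results: 2.05 + 2 = 4.05 at the earliest, 2.42 + 4 = 6.42 months at the latest.
- Last of 24 finished: 3 + 0.92 = 3.92 to 4 + 0.92 = 4.92 months.

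In every combination the results come after enrolment has closed. Only with 4 months of enrolment and a 2-month assay do they precede the last subject's final visit (4.42 against 4.92 months). So a mid-study look is hardly obtainable, as Section 6.5 says, while a later decision on an extra assay is.

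**2. What does the rule control?** CyTOF appears in the abbreviation list, in this synopsis row and in reference 27. It is in no aim, no procedure and no statistical section; the principal component analysis in Section 6.3 uses lipidomic and antibody data. The rule does not alter the number treated or the final paired tests, so their error rate is untouched.

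**3. The plan's power figure.** Power = 1 − F(t₀; n−1, d√n), where F is the noncentral t distribution function, t₀ the two-sided critical value at α = 0.05/3 = 0.0167, and d the mean change divided by the SD of the differences. At n = 9, 80% power needs d = 1.323, so for a 50% rise the SD may be at most 0.5/1.323 = 0.378 on the proportional scale. The SD is not given, so the claim can be neither confirmed nor refuted; it serves only as an anchor. A 90% anchor (d = 1.509) is an assumed upper case.

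| Pairs | Power, 80% anchor | Power, 90% anchor |
|---|---|---|
| 9 | 80% | 90% |
| 8 | 72% | 83% |
| 7 | 61% | 73% |
| 6 | 48% | 60% |

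**4. Loss among the first 9 enrolled.** With pairs ~ Binomial(9, 1 − loss) and the 80% anchor:

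| Assumed loss | All 9 pairs kept | Mean power |
|---|---|---|
| 5% | 0.95⁹ = 63% | 76% |
| 10% | 0.90⁹ = 39% | 72% |
| 25% = (24 − 18)/24 | 0.75⁹ = 7.5% | 56% |

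The last row treats the plan's full allowance for possible loss as the expected loss. All rows assume that someone counts subjects with no post sample among the 9. A rise cannot be judged without a pre/post pair, so the natural count is the first 9 with both samples, and then the table does not apply.

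**5. The criterion.** I simulated 60,000 sets of 9 pairs for three metabolites in two matrices, with equal correlation 0.5 (assumed) and d = 1.323 for a true rise. The chance that CyTOF is run is then:

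- any one of six tests significant: 97% at α = 0.05/6, or 99% at 0.05/3; with no true change, 2% and 4%;
- all three significant in PBMCs or all three in serum, at 0.05/3: 75%;
- all six significant, at 0.05/3: 44%;
- any one mean above baseline, with no test: 86% when nothing has changed.

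The last two give the alarming figures and are the least plausible readings. Requiring all six contradicts the word that joins PBMCs and serum in the rule. Accepting any higher mean ignores the paired test that the plan uses throughout.

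**6. Serum.** Serum is an Aim 1a matrix in the synopsis, the Section 2.1 heading, Section 4.1 and Section 5. Its absence from Section 3.1 is a drafting slip; the rule's matrices are both measured.

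**The case for a change.** The strongest case for a change is that no sentence exempts the rule. A reader of Sections 5.1 and 6.5 alone would not know that a subset of Aim 1a data is to be used for a decision. The benign reading has to be inferred from the safety sentence in Section 5.1 and from the absence of a date in the synopsis. The threshold for increased uptake and the way the two matrices combine are indeed unstated, and between the plausible readings the chance of running CyTOF after a true rise goes from 75% to 99%. Plasma, which Aim 1a measures, is missing from the rule without explanation, and the source of the 9 subjects for the fallback pilot is not given. A few sentences would settle all this at almost no cost.

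Those observations are correct. What they lack is a consequence for this trial. The open points decide only whether the team spends its own departmental money on an assay for which the protocol makes no claim and plans no analysis. The added sentences would record what a sensible analyst would do anyway: wait for paired results, test the three named metabolites, and decide on the assay.

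**Conclusion.** No change is called for. The difference in wording between the synopsis and Sections 5.1 and 6.5 is real but harmless. The likely meaning is a non-stopping decision about an add-on assay, made when paired results on the three named metabolites are available. The missing threshold is a gap that analysts can fill from the plan's own paired test and error rate.

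The effect on the 24-subject trial is nil: enrolment, dosing, the Aim 1 and Aim 2 tests and their error rates are the same whether CyTOF is run or not. The larger figures (56% power, 7.5% with all nine pairs, 44% and 86% for the criterion) depend on an assumed 25% loss counted against the nine or on strained readings of the rule, and should carry no weight.

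This rests on the rule not being used to stop or alter the trial, which nothing in the documents suggests, and, for timing, on even accrual and an assay time of 2-4 months. No view is taken on the length of supplementation in the fallback pilot.

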## **1 BACKGROUND AND RATIONALE**

### **1.1 Introduction**

Chronic inflammation, a central component of obesity, contributes toward the development of numerous metabolic complications such as type 2 diabetes, cardiovascular diseases, and increased susceptibility to infection. The metabolism of immune cells has emerged as a major therapeutic target for improving chronic inflammation, and thereby, whole-body metabolism. Specialized pro-resolving mediators (SPMs) in particular are lipid-derived metabolites that have been shown to orchestrate the resolution of inflammation, regeneration of damaged tissues, and even improve outcomes to infections. However, SPMs are lowered with obesity. It is therefore hypothesized that exogenous administration of SPMs to obese humans may have therapeutic value as insulin and glucose sensitizing agents by targeting chronic inflammatory pathways in obesity. Until recently, a major roadblock in the field of obesity and SPMs is that translation of findings from the preclinical level to humans has remained limited. However, this obstacle can now be overcome as the first oral formulation of SPMs has emerged on the market as a dietary supplement. We will lead the field by taking the first steps toward precision administration of SPMs as therapeutic agents for immune resolution of chronic inflammation in the obese. Specifically, we will establish the concentration of SPMs in plasma, serum and peripheral blood mononuclear cells (PBMCs) of obese subjects in response to dietary supplementation with 'SPM Active'. We will further determine the immunological fitness of the leukocyte pool, specifically examining B cell antibody production in response to ex-vivo stimulation. This will determine whether SPM supplementation mitigates the impaired humoral immune response of obese subjects. Overall, this work will help determine the use of SPMs as potential therapeutic agents for the obese.

### **1.2 Name and Description of Investigational Product or Intervention**

The study will provide the dietary supplement 'SPM Active,' manufactured by Metagenics, as intervention. Each capsule contains 145 mg of the specialized pro-resolving mediators (SPMs) 18-HEPE (25 mg), 17-HDHA (40 mg) and 14-HDHA (80 mg) from fractionated marine lipid concentrate. SPMs are synthesized enzymatically from n-3 polyunsaturated fatty acids (PUFA) known as eicosapentaenoic (EPA) and

docosahexaenoic acids (DHA) and are known to play a critical role in resolving chronic, low-grade inflammation.

